5.7 Subject Withdrawal/Discontinuation Criteria

Subjects may withdraw consent at any time for any reason or be dropped from the trial at the discretion of the investigator should any untoward effect occur. In addition, a subject may be withdrawn by the investigator or the Sponsor if enrollment into the trial is inappropriate, the trial plan is violated, or for administrative and/or other safety reasons. Specific details regarding discontinuation or withdrawal are provided in Section 7.1.4 – Other Procedures.

A subject must be discontinued from the trial treatment for any of the following reasons:

- The subject or legal representative (such as a parent or legal guardian) withdraws consent.
- Confirmed radiographic disease progression

Note: For unconfirmed radiographic disease progression, please see Section 7.1.2.5

Note: A subject may be granted an exception to continue on treatment with confirmed radiographic progression if clinically stable or clinically improved, please see Section 7.1.5.3.5.

- Unacceptable adverse experiences as described in Section 5.3
- Intercurrent illness that prevents further administration of treatment
- Investigator's decision to withdraw the subject
- The subject has a confirmed positive serum pregnancy test
- Noncompliance with trial treatment or procedure requirements
- The subject is lost to follow-up
- Administrative reasons

The End of Treatment and Follow-up visit procedures are listed in Section 6.0 (Study Flow Chart) and Section 7.1.5 (Visit Requirements). After the end of treatment, each subject will be followed for 30 days for adverse event monitoring (serious adverse events will be collected for 90 days after the end of treatment as described in Section 7.2). Subjects who discontinue for reasons other than progressive disease will have post-treatment follow-up for disease status until disease progression, initiating a non-study cancer treatment, withdrawing consent or becoming lost to follow-up. After documented disease progression each subject will be followed by telephone for overall survival until death, withdrawal of consent, or the end of the study, whichever occurs first.

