7.1.5.3.2 Safety Follow-Up Visit

The mandatory Safety Follow-Up Visit should be conducted approximately 30 days after the last dose of trial treatment or before the initiation of a new anti-cancer treatment, whichever

Product: Pembrolizumab

Protocol/Amendment No.: May 18, 2020v2.0

comes first. All AEs that occur prior to the Safety Follow-Up Visit should be recorded. Subjects with an AE of Grade > 1 will be followed until the resolution of the AE to Grade 0-1 or until the beginning of a new anti-neoplastic therapy, whichever occurs first. SAEs that occur within 90 days of the end of treatment or before initiation of a new anti-cancer treatment should also be followed and recorded. Subjects who are eligible for retreatment with pembrolizumab (as described in Section 7.1.5.3.5) may have up to two safety follow-up visits, one after the Treatment Period and one after the Second Course Phase.

The following will be performed at the **Safety Follow-Up Visit** (30 days post study treatment discontinuation):

- Collection of Demographic Information and Medical History
- Collection of Prior and Concomitant Medication Information
- Collection of Adverse Event Information
- Physical Examination
- Vital Signs
- ECOG Performance Status
- CBC with Differential
- Comprehensive Serum Chemistry Panel
- Thyroid Function Tests (T3, FT4, and TSH)

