For the time period beginning at treatment allocation/randomization through 90 days following cessation of treatment, or 30 days following cessation of treatment if the subject initiates new anticancer therapy, whichever is earlier, any serious adverse event, or follow up to a serious adverse event, including death due to any cause other than progression of the cancer under study (reference Section 7.2.. for additional details) whether or not related to the investigational product(s), must be reported within 24 hours to the Sponsor (NYU Langone Medical Center) and within 2 working days to Merck Global Safety and Eisai.

Additionally, any serious adverse event, considered by an investigator who is a qualified physician to be related to either investigational agent that is brought to the attention of the investigator at any time following consent through the end of the specified safety follow-up period specified in the paragraph above, or at any time outside of the time period specified in the previous paragraph also must be reported immediately to the Sponsor and to Merck Global Safety and Eisai.

All subjects with serious adverse events must be followed up for outcome.

Product: Pembrolizumab

Protocol/Amendment No.: May 18, 2020v2.0

SAE reports and any other relevant safety information are to be forwarded to the Merck Global Safety [contact] and

To Eisai, Inc.:

Eisai Medical Affairs
[name]
[contact]
Fax: [name]
Email: [contact]

A copy of all Reports and Progress Reports is submitted as required by FDA, European Union (EU), Pharmaceutical and Medical Devices agency (PMDA) or other local regulators. Investigators will cross reference this submission according to local regulations to the Merck Investigational Compound Number (IND, CSA, etc.) at the time of submission. Additionally investigators will submit a copy of these reports to Merck & Co., Inc. (Attn: Worldwide Product Safety; [contact]) at the time of submission to FDA.

Additionally, an FDA MEDWATCH Form 3500A (download form and instructions at <http://www.fda.gov/Safety/MEDWATCH/HowToReport/DownloadForms/ucm2007307.htm>) must be completed by the investigator and faxed to the study sponsor within 24 hours. The investigator shall maintain a copy of the MEDWATCH Form on file at the study site. If supplied as in a narrative format, the minimum information to be supplied is as follows:

- Study identifier
- Study Center
- Subject number

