Overall Survival (OS): is calculated as the interval from the start of treatment to the date of subject death (any cause).

RECIST 1.1 assessments (including Target Lesion measurements) will be used to determine ORR and PFS. Imaging assessments will be made every 6-9 weeks.

Safety Measures

AEs and SAEs will be collected throughout the study from informed consent until 30 days after study treatment is discontinued. Investigators must continue to report all SAEs to the NYU CTO until 30 days after study treatment is discontinued.

If a subject discontinues study treatment for reasons other than disease progression, and therefore continues to have tumor assessments using RECIST following the 30 days after the last dose of the last study treatment, only study drug-, or study procedure-related SAEs will be captured until the subject is considered to have progressive disease.

AEs will be graded according to the National Cancer Institute Common Terminology Criteria for AEs.

AEs will be coded using MedDRA (Medical Dictionary for Regulatory Activities).

Biomarker/Exploratory Objectives

All biomarker analyses will consist of descriptive statistical summaries at baseline (means, medians, standard deviations, quantiles, ranges, etc.) and graphical displays (e.g. boxplots). Similar summaries will be provided by changes from baseline and response status for each of the biomarkers under study. We will use non-parametric tests to assess the relationships between PDL1 status, gene expression profiles of interest, and response to combination treatment of pembrolizumab and lenvatinib. Outcome relationships will be largely explorative and descriptive.

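### Section 8.1 ends all-SAE collection 30 days after treatment, which contradicts the 90-day SAE window in Sections 5.7, 7.1.5.3.2 and 7.2.2

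*Combined protocol and SAP*

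**What the plan says.** Section 8.1, under Safety Measures, sets the collection period: "AEs and SAEs will be collected throughout the study from informed consent until 30 days after study treatment is discontinued". It then instructs sites: "Investigators must continue to report all SAEs to the NYU CTO until 30 days after study treatment is discontinued". For subjects who stop for a reason other than progression and are still being scanned after day 30, "only study drug-, or study procedure-related SAEs will be captured until the subject is considered to have progressive disease". It provides for no SAE capture after day 30 in subjects who stopped because of progression.

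The rest of the protocol uses a longer window:

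- Section 5.7 separates 30-day AE monitoring from SAEs: "serious adverse events will be collected for 90 days after the end of treatment as described in Section 7.2".
- Section 7.1.5.3.2 asks for follow-up and recording of "SAEs that occur within 90 days of the end of treatment or before initiation of a new anti-cancer treatment".
- Section 7.2.2 runs from allocation "through 90 days following cessation of treatment, or 30 days following cessation of treatment if the subject initiates new anticancer therapy", whichever is earlier. Within that window SAEs, "whether or not related to the investigational product(s), must be reported within 24 hours to the Sponsor". Related SAEs that come to light "at any time outside of the time period specified in the previous paragraph also must be reported immediately to the Sponsor".
- Section 7.2 separately asks that SAEs arising after the study period and possibly related to treatment or participation be recorded and reported at once.

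**The concern.** Section 8.1 is the statistical analysis plan, but this text does more than define an analysis window. It tells investigators what to collect and report, and it names the Clinical Trials Office as recipient. Section 7.2.2 sends SAEs to the same office. A site therefore holds two incompatible instructions for the same events and the same recipient.

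Toxicity rates belong to the secondary objective in Section 3.2. Section 5.3.1.3 recognises that pembrolizumab-associated events, serious ones included, can appear several months after the last dose. Days 31-90 are thus a period in which the protocol itself expects relevant events. The trial has more than one site (Section 5.2.2) and 29 subjects, so sites that follow different sections would supply SAE data of different scope to one small safety summary.

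**Working it through.** There is no statistical figure to reproduce. The check sets the rules side by side.

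**Inputs**

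| Section | All-SAE window after treatment | Causality scope | If new anticancer therapy starts | Related SAEs later |
|---|---|---|---|---|
| 8.1 | 30 days | All to day 30, then related only | Not addressed | Only if treatment stopped for another reason than progression, and only until progression |
| 5.7 | 90 days, deferring to Section 7.2 | No limit stated | Through Section 7.2 | Through Section 7.2 |
| 7.1.5.3.2 | 90 days | No limit stated | Refers to the time before its start | Not addressed |
| 7.2.2 | 90 days | Related or not | 30 days | At any time |

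**Step 1: length of the gap.** For a subject who starts no new anticancer therapy:

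gap = 90 - 30 = 60 days, that is days 31 to 90.

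**Step 2: which events fall in the gap.** For the same subject and the same 60 days, Sections 8.1 and 7.2.2 treat an SAE as follows:

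| Subject | SAE | 8.1 | 7.2.2 |
|---|---|---|---|
| Stopped for progression | Unrelated | Not captured | Reportable |
| Stopped for progression | Related | Not captured | Reportable |
| Stopped for another reason, not yet progressed | Unrelated | Not captured | Reportable |
| Stopped for another reason, not yet progressed | Related | Captured | Reportable |
| Stopped for another reason, since progressed | Unrelated | Not captured | Reportable |
| Stopped for another reason, since progressed | Related | Not captured | Reportable |

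The sections agree in one of the six situations and disagree in five.

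**Step 3: subjects who start new therapy.** Section 7.2.2 itself shortens the all-SAE window to 30 days, so the 60-day figure does not apply to them. Related SAEs remain reportable at any time under Section 7.2.2, so that part of the conflict persists. Section 7.1.5.3.2 words the new-therapy limit differently from Section 7.2.2.

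**Step 4: route into the analysis.** Section 8.1 summarises toxicity for each cycle and across cycles, with the highest grade across cycles as the per-patient measure. Days 31-90 after discontinuation belong to no treatment cycle. The plan therefore does not settle whether SAEs from that period enter the summary, even where they are collected.

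**The case against.** The strongest reply is that the protocol already shows where SAE timing belongs. Section 7.2 says that the reporting timeframe for serious events is set out there, and Section 5.7 defers to it. A careful site could conclude that Section 7.2.2 governs, and collection may follow it in practice. This stands in part: a reader might infer that the documents are silent on where the rule sits, and they are not. But Section 8.1 is not made subject to Section 7.2, and it instructs investigators in its own terms. The conflict remains.

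The second reply is that the planned summary is organised by cycle, so post-treatment SAEs might not appear in it even with full collection. That also stands. A reader might infer that the planned toxicity rates are shown to be too low; the documents do not establish this. It is a reason to state the handling of these events.

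Three further inferences are tempting and unsupported:

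- Section 5.4.1 records concomitant medications for SAEs beyond day 30. This is compatible with Section 8.1, which still captures some related SAEs then.
- Section 8.1 collects from consent, while Sections 7.2 and 7.2.2 limit which pre-allocation events must be reported. Broad collection with narrower reporting is not a contradiction.
- AE review at the follow-up visits in Section 7.1.5.3.3 can serve the follow-up of unresolved events and SAE ascertainment. It need not conflict with a 30-day window for new AEs.

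**Conclusion.** The contradiction is real and lies in current text. Section 8.1 gives a 30-day all-SAE window with a restricted, related-only extension, where three other sections give 90 days. Section 7.2.2 states that causality does not matter within its window. The size is 60 days per subject, on the condition that the subject starts no new anticancer therapy. For related SAEs the difference extends further, because Section 7.2.2 sets no end date.

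The documents give neither the number of SAEs expected in days 31-90 nor the share of subjects who would start new therapy, so no event count or change in a toxicity rate is claimed. The primary response analysis, sample size, alpha and power are untouched. The point should be fixed because it affects what is collected for a secondary objective.

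**What to change.** 1. In Section 8.1, delete the 30-day limit on all SAEs and the related-only restriction. Replace both with a cross-reference to Section 7.2.2 for the SAE window and causality scope.
2. In Section 8.1, state that SAEs collected after the last cycle under Section 7.2.2 are included in the safety summary, for example as a separate post-treatment row and in the per-patient maximum grade.
3. In the same edit, align the new-therapy wording in Section 7.1.5.3.2 with Section 7.2.2.

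The cost is an edit to the text plus a post-treatment row in the safety table. Section 7.2.2 already requires the data, so no new collection is added. Reported serious toxicity may rise somewhat, because events that Section 8.1 would omit will be counted.

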9.0 LABELING, PACKAGING, STORAGE AND RETURN OF CLINICAL SUPPLIES

9.1 Investigational Products

The investigator shall take responsibility for and shall take all steps to maintain appropriate records and ensure appropriate supply, storage, handling, distribution and usage of investigational product in accordance with the protocol and any applicable laws and regulations.

Product: Pembrolizumab/MK-3475
Protocol/Amendment No.: May 18, 2020v2.0

Clinical Supplies of pembrolizumab will be provided by Merck as summarized in Table 14.

Table 14: Pembrolizumab Product Description

Product Name & Potency	Dosage Form
Pembrolizumab 50 mg	Lyophilized Powder for Injection
Pembrolizumab 100 mg/ 4mL	Solution for Injection

Clinical Supplies of lenvatinib will be provided by Eisai as summarized in Table 15.

Table 15: Lenvatinib Product Description

Product Name & Potency	Dosage Form
Lenvatinib 10 mg	Capsule
Lenvatinib 4mg	Capsule

9.2 Packaging and Labeling Information

Clinical supplies will be affixed with a clinical label in accordance with regulatory requirements.

9.3 Clinical Supplies Disclosure

This trial is open-label; therefore, the subject, the trial site personnel, the Sponsor and/or designee are not blinded to treatment. Drug identity (name, strength) is included in the label text; random code/disclosure envelopes or lists are not provided.

9.4 Storage and Handling Requirements

Clinical supplies must be stored in a secure, limited-access location under the storage conditions specified on the label.

Receipt and dispensing of trial medication must be recorded by an authorized person at the trial site.

Clinical supplies may not be used for any purpose other than that stated in the protocol.

9.5 Returns and Reconciliation

The investigator is responsible for keeping accurate records of the clinical supplies received from Merck and Eisai, the amount dispensed to and returned by the subjects and the amount remaining at the conclusion of the trial.

Upon completion or termination of the study, all unused and/or partially used investigational product will be destroyed at the site per institutional policy. It is the Investigator's responsibility to arrange for disposal of all empty containers, provided that procedures for proper disposal have been established according to applicable federal, state, local and institutional guidelines and procedures, and provided that appropriate records of disposal are kept.

10.0 ADMINISTRATIVE AND REGULATORY DETAILS

10.1 Confidentiality

All samples will be stored in a secure place. Samples will be identified by a unique identifier. The subject's name will not be used on the sample. This unique identifier will be put into the sponsor database and will link in the sponsor database only to de-identified subject data (subject number). Personal health information (PHI) will not be identifiable in the sponsor database or on the stored samples. Besides protecting confidentiality, this system will allow the sponsor to destroy the sample if the subject requests this. Samples will be retained and used until they are exhausted. The log to PHI will be maintained at the study site. Information will be stored in a secure, locked room and in a secure, password-protected database. Only approved study personnel will have access to the samples.

The informed consent form (ICF) will incorporate (or, in some cases, be accompanied by a separate document incorporating) wording that complies with relevant data protection and privacy legislation.

Confidentiality and HIPAA

Information about study subjects will be kept confidential and managed according to the requirements of the Health Insurance Portability and Accountability Act of 1996 (HIPAA). Those regulations require a signed subject authorization informing the subject of the following:

- What protected health information (PHI) will be collected from subjects in this study
- Who will have access to that information and why
- Who will use or disclose that information
- The rights of a research subject to revoke their authorization for use of their PHI.

In the event that a subject revokes authorization to collect or use PHI, the investigator, by regulation, retains the ability to use all information collected prior to the revocation of subject authorization. For subjects that have revoked authorization to collect or use PHI, attempts should be made to obtain permission to collect at least vital status (i.e. that the subject is alive) at the end of their scheduled study period.

10.2 Compliance with Financial Disclosure Requirements

Any investigator who has a conflict of interest with this study (patent ownership, royalties, or financial gain greater than the minimum allowable by their institution, etc.) must have the conflict reviewed by a properly constituted Conflict of Interest Committee with a Committee-sanctioned conflict management plan that has been reviewed and approved by the study sponsor prior to participation in this study. All NYULMC investigators will follow the applicable University conflict of interest policies.

10.3 Ethical Considerations, and Compliance with Law, Audit and Debarment

This study will be performed in accordance with ethical principles that have their origin in the Declaration of Helsinki and are consistent with International Conference on Harmonisation (ICH), US government regulations, international standards of Good Clinical Practice (GCP), applicable regulatory requirements, the sponsor policy on Bioethics and Human Biological Samples, and applicable institutional research policies and procedures.

This protocol and any amendments will be submitted to a properly constituted Institutional Review Board (IRB) in agreement with local legal prescriptions, for formal approval of the study conduct. The decision of the IRB concerning the conduct of the study will be made in writing to the investigator and a copy of this decision will be provided to the sponsor before commencement of this study. The investigator should provide a list of IRB members and their affiliate to the sponsor.

All subjects for this study will be provided a consent form describing this study and will be provided sufficient information to make an informed decision about their participation in this study. This consent form will be submitted with the protocol for review and approval by the IRB for the study. The formal consent of a subject, using the IRB-approved consent form, must be obtained before that subject undergoes any study procedure. The consent form must be signed by the subject or legally acceptable surrogate, and the investigator-designated research professional obtaining the consent. The consenting process and documentation will follow Standard Operating Procedures of the NYU PCC CTO.

Treating investigators will obtain informed consent after explaining the study and answering all questions the subject or subject's legally authorized representative may have. Individuals who are authorized to obtain consent will be listed on the FDA form 1572, and may also be listed in the protocol and consent form document. If necessary, a translator and consent form in the subject's native language will be provided.

An IRB must approve the final study protocol, including the final version of the Informed Consent Form and any other written information to be provided to the subjects. The

Product: Pembrolizumab/MK-3475

Protocol/Amendment No.: May 18, 2020v2.0

investigator will ensure the distribution of these documents to the applicable IRB, and to the study site staff.

The opinion of the IRB must be given in writing. The investigator must submit the written approval to the NYU CTO before enrollment of any subject into the study.

The IRB must approve all advertising used to recruit subjects for the study.

The NYU CTO must approve any modifications to the Informed Consent Form that are needed to meet local requirements.

The NYU CTO will provide Principal Investigators with safety updates/reports according to local requirements.

Progress reports and notifications of serious and unexpected adverse drug reactions will be provided to the IRB according to local regulations and guidelines.

